4.2 Rationale for dose/regimen and duration of treatment

Previous studies have shown that a 300 mg dose of inclisiran sodium is well tolerated and provides maximum efficacy (i.e., doses higher than 300 mg did not provide additional efficacy in LDL-C lowering). The 300 mg dose of inclisiran will be administered on Day 0, Day 90 and Day 270, consistent with the dose and dosing regimen that was studied in the Phase III trials. Modelling and simulation have demonstrated that the 300 mg dose of inclisiran results in sustained reductions in LDL-C (Ray et al 2017). A treatment duration of one year will be sufficient to assess changes in LDL-C due to inclisiran and changes in concomitant lipidlowering therapy.

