6.1.4 Treatment duration

The planned duration of treatment is 330 days from randomization. Participants may be discontinued from treatment at any time due to adverse events, disease progression and/or at the discretion of the investigator or the participant.

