6.3.2 Treatment assignment, randomization

The randomization numbers will be generated using the following procedure to ensure that treatment assignment is unbiased and concealed from participants and investigator staff. A participant randomization list will be produced by the IRT system provider using a validated system that automates the random assignment of participant numbers to randomization numbers. These randomization numbers are linked to the different treatment groups, which in turn are linked to medication numbers. A separate medication list will be produced by or under the responsibility of Novartis Drug Supply Management using a validated system that automates the random assignment of medication numbers to the package containing the investigational drug(s).

At Visit 2/Baseline, all eligible participants will be randomized via Interactive Response Technology (IRT) to one of the two treatment groups in 1:1 ratio (inclisiran + usual care vs usual care). The investigator or his/her delegate will contact the IRT after confirming that the participant fulfills all the inclusion/exclusion criteria. The IRT will assign a randomization number to the participant, which will be used to link the participant to a treatment group and will specify a unique medication number for the first package of study treatment to be dispensed to the participant.

The randomization scheme for participants will be reviewed and approved by a member of the Novartis Biometrics group.

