6.5 Dose escalation and dose modification

Dose interruptions for the investigational study medication (inclisiran) are not permitted.

If a planned dose is missed by less than 3 months, administer inclisiran and maintain dosing according to the participant's original schedule. If a planned dose is missed by more than 3 months, start a new dosing schedule - administer inclisiran initially, again at 3 months, and followed by dosing, thereafter, every 6 months.

Dose interruptions must be recorded on the inclisiran Dose Administration case report form for the investigational study drug.

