2.1.1 General definitions

Study treatment

The following are the investigational treatments:

- Inclisiran (KJX839), 284 mg, 1.5 ml liquid in a single-use prefilled syringe (PFS) for s.c. administration plus usual care
- Usual care alone

The following treatment labels will be used for all tables, listings and figures:

- Inclisiran + Usual Care
- Usual Care

Study treatment start and end date

Study treatment start date is defined as the first date when a non-zero dose of study drug is administered for the inclisiran + usual care group. If a participant, who is randomized to the inclisiran + usual care group, does not take any study drug then treatment start date will be the randomization date.

For the usual care alone group the study treatment start date will be the randomization date.

“Day 1” will be used to identify study treatment start date for both treatments.

Study treatment end date is defined as the treatment phase completion date recorded on the “Treatment Disposition” CRF for inclisiran + usual care participants. For the usual care alone group, the study treatment end date is the last recorded contact/participation date in the database.

Study start and end date

Study start date is defined as the first date when a non-zero dose of study drug is administered for the inclisiran + usual care group. If a participant, who is randomized to the inclisiran + usual care group, does not take any study drug then study start date will be the randomization date.

For the usual care alone group the study start date will be the randomization date.

Study end date is defined as the date of last recorded contact/participation date in the database.

Duration of exposure to inclisiran

For the inclisiran + usual care group, duration of exposure to inclisiran (in days) is defined as the number of days from Day 1 to the study *treatment* end date. Duration of exposure will not be defined for the usual care alone group.

Planned and actual treatment definitions

The following definitions will be used for planned and actual treatment.

Table 2-1 Planned and Actual Treatment Definitions

Randomized Treatment Group	Inclisiran Use Scenario During Study (Inclisiran Use Recorded as Study Treatment or Concomitant Medication)	Planned Treatment	Actual Treatment
Inclisiran + Usual Care	Received at least one dose of inclisiran	Inclisiran + Usual Care	Inclisiran + Usual Care
Inclisiran + Usual Care	Never received inclisiran	Inclisiran + Usual Care	Usual Care

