2.7.1 Adverse events (AEs)

The Medical Dictionary for Regulatory Activities (MedDRA) dictionary will be used for coding AEs, and up-versioning will be applied during the course of study. The final MedDRA version used in this study will be v27.0. Partially missing AE dates will be imputed following Appendix 5.1.2. An AE (classified as preferred term) occurring during the treatment period will be counted as a treatment-emergent AE (TEAE) either if it is not present at Day 1 before treatment or if it is present before treatment but increased in severity during the treatment period. Therefore, all recorded AEs with onset on or after the study treatment start date will be counted as TEAE. In case the AE date values do not allow unequivocally allocating an AE record to TEAE or non-TEAE, the AE will be considered as TEAE in the statistical analysis. The following summary tables will be presented:

- Overall Summary of TEAEs
- TEAEs by System Organ Class (SOC) and Preferred Term (PT)
- TEAEs by PT
- Common ($\geq 3\%$ within either treatment group) by PT
- TEAEs by SOC, PT, and Severity
- TEAEs by SOC, PT, and Relationship to Study Treatment
- Related TEAEs by SOC, PT, and Severity
- Treatment Emergent Serious AEs (TESAEs) by SOC and PT
- TESAEs by PT
- TESAEs by SOC, PT, and Severity
- TESAEs by SOC, PT, and Relationship to Study Treatment
- Related TESAEs by SOC, PT, and Severity
- TEAEs Leading to Withdrawal of Study Treatment by SOC and PT
- TEAEs with a Fatal Outcome by SOC and PT

If more than one event occurred with the same PT for the same participant, the participant will be counted only once for that PT using the most severe or related occurrence for the summary by severity, or relationship to study drug, respectively.

Missing severity and relationship will not be imputed and will be identified as 'missing' in the tables.

For common (3% within either treatment group) TEAEs, serious TEAEs and TEAEs leading to withdrawal of study treatment, risk ratios along with 95% confidence intervals will be presented to compare treatment groups with respect to risk.

For tables presented by SOC and PT, system organ classes are sorted alphabetically and within each system organ class, the preferred terms are sorted in descending order of total frequency.

For tables presented by PT, preferred terms are sorted in descending order of total frequency.

Listings will be presented for participants with SAEs and AEs leading to discontinuation of study treatment.

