2.12 Other Exploratory analyses

The exploratory efficacy variables are the following:

8. Cardiovascular death (yes, no)
9. Non-fatal MI (yes, no)
10. Resuscitated cardiac arrest (yes, no)
11. Non-fatal ischemic stroke (yes, no)
12. Composite MACE (cardiovascular death, non-fatal MI, resuscitated cardiac arrest, or non-fatal ischemic stroke) (yes, no)

[REDACTED]

[REDACTED]

[REDACTED]

Exploratory efficacy variables 8-12 will be summarized descriptively by total number of events and number and percentage of subjects with any event for each treatment group. In addition, a time-to-event analysis will be carried out. Time to first occurrence of any event in the composite MACE as well as time to first occurrence of each of its components will be derived as study day of onset of the corresponding TEAE, imputing for partially missing dates as needed. Adverse events with missing onset date will not be considered in the time-to-event analysis. Cox proportional hazards models will be used to estimate the corresponding hazard ratios of inclisiran + usual care over usual care with associated 95% confidence intervals. Treatment and baseline LDL-C will be used as explanatory variables in the Cox proportional hazards models. Observation time for participants without the respective event will be censored at their end of study date (date of last participation) or date of death, as applicable.

[REDACTED]

[figure not shown]
[REDACTED]

[REDACTED]

Table 2-6 MACE Definitions (using TEAEs only)

Category	Details
Cardiovascular death	(1) Fatal SAEs in "Cardiac disorders" SOC (2) Fatal SAEs in "General disorders and administration site conditions" SOC: PTs "Death", "Sudden cardiac death", "Cardiac death", "Apparent death" (3) Central nervous system haemorrhages and cerebrovascular accidents (HLT), fatal events only
Non-fatal MI	Myocardial infarction (SMQ, broad and narrow search), non-fatal events only, excluding PT "Blood creatine phosphokinase increased"
Resuscitated cardiac arrest	PT "Cardiac arrest", non-fatal events only

Non-fatal ischemic stroke	PT "Ischaemic stroke", non-fatal events only
---------------------------	--

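### SAP 2.1.1 starts the study clock at first dose in the inclisiran arm but at randomization in usual care; a late first dose would drop early MACE in one arm and, under further conditions, move the Day 330 LDL-C out of its window

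*Protocol*

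**What the plan says.** Protocol 6.1.4 measures the treatment period from randomization in both arms: "The planned duration of treatment is 330 days from randomization". Randomization takes place at Visit 2 (Protocol 6.3.2). The first injection is planned for the same visit: "The 300 mg dose of inclisiran will be administered on Day 0, Day 90 and Day 270" (Protocol 4.2), and Table 8-1 puts both in the Baseline column.

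SAP 2.1.1 then sets the start date by arm. For inclisiran: "Study treatment start date is defined as the first date when a non-zero dose of study drug is administered". For usual care: "For the usual care alone group the study treatment start date will be the randomization date". An inclisiran participant who is never dosed reverts to the randomization date. Study start date is defined in the same way.

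Several analyses depend on these dates:
- study day, the baseline cut-off and the windows of SAP Table 2-2 (Day 270: study days 181-300, target 271; Day 330: study days 301-375, target 331);
- duration on study, which is the denominator of secondary variable 22 (SAP 2.3.1 and 2.6.2);
- treatment-emergent status: "all recorded AEs with onset on or after the study treatment start date will be counted as TEAE" (SAP 2.7.1);
- MACE, which Table 2-6 builds from TEAEs only and whose time to first event "will be derived as study day of onset of the corresponding TEAE" (SAP 2.12).

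Protocol 8.5.1 describes MACE as assessed over the course of the trial, with no condition on dosing. SAP section 4 records that Day 0 is relabelled Day 1 but does not record an origin that differs by arm. On missed doses Protocol 6.5 says: "If a planned dose is missed by less than 3 months, administer inclisiran", and keeps the participant on the original dosing schedule. It does not mention the first dose.

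**The concern.** The Full Analysis Set follows the intention-to-treat principle, so time zero should be the same event in both arms. Here it is randomization in usual care and a post-randomization event in the inclisiran arm. When the two dates differ, the inclisiran participant has a stretch of randomized follow-up that is outside the analysis, while the same stretch counts in usual care.

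Two results could be affected. The MACE comparison would omit early inclisiran events, soon after an ACS, a period that Protocol 4.1 itself describes as high risk. The Day 330 LDL-C, on which both primary variables rest, could be assigned to the wrong analysis visit. These act in opposite directions: the first favors inclisiran and the second counts against it on variable 2. They concern different endpoints, so one does not offset the other.

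**Working it through.** **Inputs.** Study day = event date - study treatment start date + 1 (SAP 2.1.1). Windows are from SAP Table 2-2. Visit 4 is at Day 270 and Visit 5 at Day 330 (Protocol Table 8-1), with a tolerance of +/- 7 days (Protocol section 8). There are 192 participants per arm (Protocol 12.8.1). Let d be the days from randomization to first dose.

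**1. The plan's own figure.** With d = 0, Visit 5 has study day 330 - 0 + 1 = 331, the target in Table 2-2. On-schedule dosing gives the same clock in both arms.

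**2. MACE.** A new non-fatal event between randomization and a late first dose has its onset before the start date. It is not a TEAE, so Table 2-6 does not count it. The same event in usual care is counted. The excluded follow-up is d days per late-dosed participant: 30/330 = 9.1% of the period at d = 30, and 60/330 = 18.2% at d = 60. Some events are kept: an event that worsens after dosing can still be treatment-emergent, and a participant who dies or stops before any dose reverts to the randomization date.

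**3. Variable 22.** Duration on study starts d days later in the inclisiran arm, so about 330 - d days are assessed instead of 330. The documents do not allow a direction or size to be derived.

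**4. Day 330 LDL-C, if visits stay on the randomization calendar.** Visit 5 has study day 331 - d.
- d = 30: study day 301, inside the Day 330 window.
- d = 31: study day 300, inside the Day 270 window.
- Visit 5 held 7 days early: 324 - d <= 300 when d >= 24.
- Visit 5 held 7 days late: 338 - d <= 300 when d >= 38.

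The SAP keeps the value closest to target. With both visits on schedule and d = 31, Visit 5 is 300 - 271 = 29 days from target 271. Visit 4 has study day 271 - 31 = 240, which is 31 days away. Visit 5 therefore replaces Visit 4 and enters the MMRM as Day 270. Unless another sample falls in study days 301-375, Day 330 is missing. SAP 2.5.4 scores that as non-response for variable 2 and treats it as missing at random for variable 1.

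**5. Size per participant.** 1/192 = 0.0052, so each displaced participant lowers the inclisiran response rate by at most 0.52 percentage points. The maximum applies only if that person would have been a responder.

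**6. Illustration with assumed shares.** The documents give no delay rate. Suppose 1%, 2% or 5% of the inclisiran arm (about 2, 4 or 10 of 192) is displaced. The planned rate of 0.75 becomes 0.75 x (1 - share) = 0.7425, 0.735 or 0.7125. Against 0.55, with 192 per arm and two-sided alpha 0.025, power for variable 2 goes from 0.972 to 0.959, 0.942 or 0.859. This leaves out any non-response from the planned 20% loss to follow-up. For variable 1 (difference 15, SD 40, 153 per arm before displacement) power goes from 0.850 to 0.849, 0.847 or 0.840. The planned totals of 306 and 242 reproduce, and 306/0.8 = 382.5 is consistent with 384. None of them depends on this point.

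**The case against.** The case on the other side is substantial.

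- **Planned conduct gives no discrepancy.** Randomization and first dose share Visit 2, and the IRT issues the first kit number at randomization. Protocol 6.1.4 concerns treatment duration, and Day 0 in Table 8-1 is equally the randomization day and the dose day. This stands. A reader might infer that protocol and SAP contradict each other outright; the documents do not support that.
- **Late first doses are not clearly foreseen.** The SAP fallback covers participants never dosed, and Protocol 6.5 is a general rule that does not mention the first dose. It stands that this shows a possibility only.
- **The protocol's own TEAE definition (12.5.2) also starts at first dose.** This stands for the general adverse event tables. It does not settle MACE, which Protocol 8.5.1 assesses throughout the trial.
- **MACE is exploratory, and a displaced LDL-C is conservative for variable 2.** Both are true and limit the weight of the point. Neither justifies a different origin in each arm.
- **A randomization clock can fail too.** Table 6-4 spaces doses relative to one another. If visits were moved to follow the dose, Visit 5 would have randomization-based study day 331 + d, which exceeds 375 at d >= 45. That fits poorly with keeping the original schedule under Protocol 6.5, but the protocol does not say which calendar applies. The window part of the fix therefore needs a nominal-visit rule; the MACE part does not.

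A reader might also infer that a post-randomization baseline is likely in the inclisiran arm. No LDL-C draw is scheduled between Day 0 and Day 90, so it would take an unscheduled central-laboratory sample or a delay running to about Visit 3.

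**Conclusion.** The point holds as a conditional defect in the SAP's definitions. The time origin differs by arm and is not disclosed as a change. For any inclisiran participant dosed after the randomization date, new non-fatal MACE in the gap is excluded in that arm only, and duration on study for variable 22 starts later.

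Misassignment of the Day 330 LDL-C needs three further conditions: a delay of at least 31 days (24 if Visit 5 is 7 days early), visits kept on the randomization calendar, and no other sample in study days 301-375. Even then the value is moved, not deleted: with visits on schedule it enters the MMRM as Day 270, and it remains in the descriptive Day 330/Last Visit tables.

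The size is unknown and probably small. The bound of 0.52 percentage points per displaced participant is firm; the 1% to 5% shares are assumptions. It would be tempting to say that late-dosed participants lose early events, or that a given number of events will be missing. The documents support neither. A delay excludes follow-up time, and an event is excluded only if one occurs in that time.

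**What to change.** In SAP 2.1.1 and 2.12, before database lock:

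- Use the randomization date as the common origin in both arms for time to MACE, baseline and study duration for variable 22. Count all MACE from randomization, not only those that are TEAEs.
- Use randomization-based study day for the analysis windows. Add that the nominal Visit 5 LDL-C is assigned to Day 330 if a late first dose shifts the visit calendar. On the randomization calendar Visit 5 then falls on study days 324 to 338 with the 7-day tolerance, inside 301-375 whatever the delay.
- Keep the first-dose date for inclisiran exposure, injection-site events and the general TEAE tables, in line with Protocol 12.5.2.
- If the arm-specific origin is retained anywhere else, list it in SAP section 4.

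The cost is a small change to the derivations, and MACE before a late first dose will count in the inclisiran arm. Sample size is unaffected. If every first dose was given on the day of randomization, results are identical.

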6.2 Other treatment(s)

Not applicable

6.2.1 Concomitant therapy

All prior cardiovascular medications (e.g., antiplatelets (aspirin, thienopyridines), non-vitamin K oral anticoagulants (NOACs), beta-blockers, ACE-inhibitors or ARBs, other antihypertensives, antidiabetics, and lipid lowering therapies) administered before the

participant is enrolled in the study but still receiving must be recorded in the appropriate Case Report Forms, or where applicable, sourced from the EHR and mapped into the clinical study.

All medications, procedures, and significant non-drug therapies (including physical therapy and blood transfusions) administered after the participant is enrolled into the study must be recorded on the appropriate Case Report Forms.

Each concomitant drug must be individually assessed against all exclusion criteria/prohibited medication. If in doubt, the investigator should contact the Novartis medical monitor before randomizing a participant or allowing a new medication to be started. If the participant is already enrolled, contact Novartis to determine if the participant should continue participation in the study.

6.2.1.1 Permitted concomitant therapy requiring caution and/or action

Not applicable

6.2.2 Prohibited medication

The treatments displayed in the table below are not allowed to be used simultaneously with inclisiran in the treatment arm. No modifications of therapy is required or recommended in the usual care arm.

Medication	Prohibition period	Action to be taken
Alirocumab (Praluent)	Participants randomized to inclisiran: monoclonal antibodies directed against PCSK9 are prohibited for the full duration of the study	Discontinue PCSK9 inhibitor
Evolocumab (Repatha)	Participants randomized to inclisiran: monoclonal antibodies directed against PCSK9 are prohibited for the full duration of the study	Discontinue PCSK9 inhibitor

Table 6-2 Prohibited medication

6.3 Participant numbering, treatment assignment, randomization

6.3.1 Participant numbering

Each participant is identified in the study by a Participant Number (Participant No.), that is assigned when the participant is enrolled for screening and is retained for the participant throughout his/her participation in the trial. A new Participant No. will be assigned at every subsequent enrollment if the participant is re-screened. The Participant No. consists of the Center Number (Center No.) (as assigned by Novartis to the investigative site) with a sequential participant number suffixed to it, so that each participant's participation is numbered uniquely across the entire database. Upon signing the informed consent form, the participant is assigned to the next sequential Participant No. available to the site.

6.3.2 Treatment assignment, randomization

The randomization numbers will be generated using the following procedure to ensure that treatment assignment is unbiased and concealed from participants and investigator staff. A participant randomization list will be produced by the IRT system provider using a validated system that automates the random assignment of participant numbers to randomization numbers. These randomization numbers are linked to the different treatment groups, which in turn are linked to medication numbers. A separate medication list will be produced by or under the responsibility of Novartis Drug Supply Management using a validated system that automates the random assignment of medication numbers to the package containing the investigational drug(s).

At Visit 2/Baseline, all eligible participants will be randomized via Interactive Response Technology (IRT) to one of the two treatment groups in 1:1 ratio (inclisiran + usual care vs usual care). The investigator or his/her delegate will contact the IRT after confirming that the participant fulfills all the inclusion/exclusion criteria. The IRT will assign a randomization number to the participant, which will be used to link the participant to a treatment group and will specify a unique medication number for the first package of study treatment to be dispensed to the participant.

The randomization scheme for participants will be reviewed and approved by a member of the Novartis Biometrics group.

